4.6 Exposure

4.6.1 Definition of vaccination status

- Unvaccinated: absence of records of vaccination with PCV13 or PPSV23 in the vaccination registry or medical records, or if the vaccine dose was given less than 14 days prior to onset of symptoms;
- Vaccinated with PCV13: individuals that have received at least one dose PCV13 at least 14 days before onset of symptoms;
- Vaccinated with PPSV23: individuals who have received at least one dose of PPSV23 at least 14 days before onset of symptoms regardless the age and time since vaccination;

TECHNICAL DOCUMENT – Protocol on effectiveness of Pneumo vaccines in elderly

- Vaccinated with both PCV13 and PPSV23: individuals who have received both vaccines, the last one received at least 14 days before onset of symptoms, regardless the age and time since vaccination with the first provided vaccine;
- Repeated vaccination with PPV23: individuals who received more than one dose of PPV23, the
 last one at least 14 days before onset of symptoms regardless the age and time since
 vaccination;
- Uncertain vaccination history: individuals with no vaccination information available (no written
 medical records or no registry available, brand name not mentioned, date of administration
 unknown) or vaccinated during a clinical trial.

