4.6.2 Vaccination status ascertainment

The exposure of interest in this study is the history of vaccination with any of PPSV23 or PCV13 vaccines. The vaccination history includes number of doses, date of administration of each dose and brand of each vaccine.

Vaccination status is extracted from available data sources: vaccination registry, hospital or family physicians medical records, or vaccination cards. Efforts should be made to validate the vaccination status. Information on individuals with no information on vaccination status is collected and considered for the sensitivity analysis.

► Each study site to describe the quality and source of the vaccination data and whether they plan to validate the vaccination ascertainment using other sources or studies (vaccination survey, etc.).

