Vaccine coverage can be measured using different population sub-groups (from now on called reference groups). The best reference group will be the one representing the vaccination coverage in the population giving rise to the cases.

The size of the reference group should be large (> 1000 individuals).

Examples of sources for vaccination coverage include:

- For GPs with computerised medical records, vaccination coverage can be extracted from the GP's database;
- For GPs without computerised medical records, a sample of patients in a defined time period may be selected and influenza vaccination status documented;
- For GPs without computerised medical records, a sample of the population in the catchment area can be selected and interviewed on their influenza vaccination status (telephone, face to face):
 - Vaccination registries;
 - Health insurance claims data;
 - National surveys;
 - Vaccines distributed, vaccines sales in pharmacies.

Analysis

Measure of effect

When looking within populations where the coverage represents the same population as the cases, the VE against each of the outcomes selected (e.g IPD, SpCAP or pneumococcus serotype outcome) can be calculated as 1- odds of vaccination in cases / odds of vaccination in the population, or:

in which PPV is the proportion of the reference group vaccinated (vaccine coverage in the reference group), and PCV the proportion of influenza cases vaccinated.

Ninety five percent confidence intervals will be computed using the Farrington method²⁴.

TECHNICAL DOCUMENT – Protocol on effectiveness of Pneumo vaccines in elderly

²⁴ Farrington CP. Estimation of vaccine effectiveness using the screening method. Int J Epidemiol. 1993 Aug;22(4):742–6.

Stratified analysis

Analysis will be stratified according to the availability of vaccination coverage in the reference group:

- age groups (<75 and >74 years);
- underlying conditions

These analyses could only be performed if appropriate sample size in each stratum could be reached.

Adjusted analysis, Farrington method

Each case is matched to the coverage from the population that best matches that case according to key confounding variables such as age, chronic conditions and time period. The analysis is then performed as a logistic regression with an offset as the logit of the matched coverage²⁵.

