These variables are included in the model to look at the interaction and define if there is effect modification. If effect modification is identified, then a stratified analysis will be conducted. The analysis can be done only if PCV and PPV are available by the effect modifiers strata:

Logit [PCV] = logit[PPV] + a +
$$b_xX_x$$
 +... b_kX_k

An adjusted VE and its 95% CI will be obtained.

► Each study site to describe additional studies used to validate the indirect cohort method.

-

²⁵ Idem 24

Version number	Date published	Text in original document	Changes included in the amended version	Comments
V2.1	15 Dec 2016	Page 14 (secondary outcomes) Page 14 (Case definitions for secondary outcomes) Table 3 "Clinical presentation (meningitis, pneumonia, sepsis)"	Modified by "Clinical presentation (meningitis, bacteraemic pneumonia, bacteraemia, other clinical presentations)"	Note that bacteraemia covers all bacteremia and not only bacteremia without focus (because in Denmark no difference between pneumonia and bacteremic pneumonia can be made) Decision during the technical meeting (Paris, September 2016) because the definition of sepsis is not homogenous over the sites.
		Page 15 (Case definitions for secondary outcomes and reference group) "Severity is assessed according to: ICU admission and/or length of hospital stay >14 days and/or presence of septic shock and/or intra-hospital death"	Modified as: "Severity is assessed according to: ICU admission and/or length of hospital stay >14 days and/or death within 30 days"	Decision during the technical meeting (Paris, September 2016
		Page 17: Definition of vaccination status	Included a definition for repeated vaccination	Decision during the technical meeting (Paris, September 2016)
		Page 17-18: confounders and effect modifiers Table 4: text replaced by the ICD codes for risk conditions	Modified to include the ICD codes for the underlying conditions	Decision during the technical meeting (Paris, September 2016)

		Table 4 ICD codes for IPD and SpCAP	Table 4 becomes table 2 and includes ICD codes for clinical IPD and SpCAP	Decision during the technical meeting (Paris, September 2016)
		Table 4: ICD codes for the underlying conditions by immune status	The new table 4 includes ICD 9 and 10 codes for underlying conditions	Decision during the technical meeting (Paris, September 2016)

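### Appendix 1 allows reference coverage from dose counts or interviews without matching how cases are ascertained, so the screening VE can err in either direction by as much as the bias it should detect

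*Protocol*

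**What the plan says.** **Cases.** Section 4.6.2 states: "Vaccination status is extracted from available data sources: vaccination registry, hospital or family physicians medical records, or vaccination cards". The history includes number of doses, dates and brand. Section 4.6.1 treats the lack of a record as no vaccination: "Unvaccinated: absence of records of vaccination with PCV13 or PPSV23 in the vaccination registry or medical records". A dose within 14 days of onset does not count. Any earlier PPSV23 dose does count, whatever the age or interval, so exposure is cumulative. The same section has a separate category for "individuals who received more than one dose of PPV23".

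**Reference.** Appendix 1 opens by asking that the NVT control group be checked against other control groups drawn from the same data sources. Under Vaccine coverage in the reference group it asks for more than 1000 individuals who represent the population giving rise to the cases. It then gives a list headed "Examples of sources for vaccination coverage include". The list contains GP databases, registries and claims data. It also contains national surveys, "Vaccines distributed, vaccines sales in pharmacies", and a population sample that "can be selected and interviewed on their influenza vaccination status (telephone, face to face").

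**Estimator.** Measure of effect defines VE as 1 minus the odds of vaccination in cases divided by the odds in the reference population.

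**The concern.** The screening VE is a ratio of two odds, one from the cases and one from the reference. If vaccination is measured differently on the two sides, the difference passes straight into VE, even when the reference population is perfectly representative. The appendix's cautions concern who is covered and over what period. None concerns how vaccination is measured.

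A dose count departs from the case definition in both directions. Repeat PPSV23 doses, unused doses and doses given to people under 65 make coverage look too high. A sales window shorter than the vaccination history, or a count of pharmacy sales alone, makes it look too low. An interview can err either way.

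The comparator exists to judge whether the NVT controls are sound. If its own error is of the size of the bias under test, disagreement need not mean the controls are wrong, and agreement need not mean they are right.

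**Working it through.** **The protocol's own benchmark.** Section 6.1 gives VE_Broome = 1 − (1 − VE)/(1 + VEc × Pu/(1 − Pu)), with Pu = 0.40.
- VE 90%, VEc 50%: 1 − 0.10/1.3333 = 92.5%. Reproduced.
- VE 70%, VEc 30%: 1 − 0.30/1.2 = 75%. Reproduced.

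The protocol gives no figure for the screening method.

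**Inputs.**
- True VE 60%: the average that Section 1.1 quotes for PPSV23 against vaccine-type IPD in those aged 65 and over.
- True coverage c of 30%, 50% and 70%: from Table 4, Section 4.8.
- Errors in the reference (assumptions, not in the documents): stated coverage 10% or 25% too high, or 20% too low; interview sensitivity 0.90 and specificity 0.85 against the record.
- Cases taken as correctly classified, so odds in cases = 0.4 × odds(c).

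**Formula.** Screening VE = 1 − 0.4 × odds(c)/odds(c_obs), where c_obs is the coverage read from the source.

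Examples:
- c = 0.30, 25% too high: c_obs = 0.375; 1 − 0.4 × 0.4286/0.6 = 71.4%.
- c = 0.50, 20% too low: c_obs = 0.40; 1 − 0.4 × 1/0.6667 = 40.0%.
- Interview, c = 0.70: c_obs = 0.7 × 0.90 + 0.3 × 0.15 = 0.675; 1 − 0.4 × 2.3333/2.0769 = 55.1%.

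| Reference error (true VE 60%) | c = 30% | c = 50% | c = 70% |
|---|---|---|---|
| 10% too high | 65.2% | 67.3% | 72.1% |
| 25% too high | 71.4% | 76.0% | 86.7% |
| 20% too low | 45.7% | 40.0% | 26.7% |
| Interview 0.90/0.85 | 71.4% | 63.8% | 55.1% |

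The interview error is zero where 0.90c + 0.15(1 − c) = c, that is c = 0.15/0.25 = 60%, and it changes sign above that.

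**Can the check hide the bias?** With VEc 30% and Pu 40%, replacement divides the indirect-cohort odds ratio by 1.2. At true VE 60%, VE_Broome = 1 − 0.4/1.2 = 66.7%. A 10% overstatement at 50% coverage gives a screening VE of 67.3%: the two agree and both are about 7 points too high. Exact agreement needs odds(c_obs) = 1.2 × odds(c), which is an overstatement of 13% at c = 30%, 9% at 50% and 5% at 70%.

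**Can it raise a false alarm?** If the NVT controls are sound, the indirect cohort gives 60%. Coverage 20% too low gives 45.7% or 40.0% at 30% or 50% coverage, a gap of 14 to 20 points that comes from the source alone.

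**With matched sources.** Suppose cases and reference are both read from records with sensitivity 0.9 (assumed) and perfect specificity. At c = 30%, recorded coverage is 0.27 in the reference and 0.9 × 0.1463 = 0.1317 in cases, so VE = 59.0%. At c = 50% it is 57.7%. NVT controls read from the same records carry the same error, so it cancels in the comparison of methods.

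**The case against.** The list gives examples in a generic protocol that sites adapt, and it already contains record-based sources. The appendix asks for a reference that represents the cases' source population, and its size rule presupposes individuals. Section 6.2.3 has each site describe bias in ascertaining vaccination status, and the main indirect-cohort estimate does not use this comparator. All of that stands: it limits the weight of the point and means that VE *can* be biased, not that it *is*. It does not remove the point. The appendix still names sources that fail its own same-source and individual-count conditions, and no instruction requires like ascertainment.

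A reader might infer that the bias runs mostly upward. The documents do not support that. They give no error rates, cumulative exposure leaves room for undercounting, and the interview example above reverses sign at 60% coverage.

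A reader might also infer that sales data break the adjusted analysis because they lack strata. The appendix covers this: "The analysis can be done only if PCV and PPV are available by the effect modifiers strata", where the two abbreviations are the proportions vaccinated in cases and in the population. Without strata, that analysis is simply not done.

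Finally, the interview item names influenza vaccination, so read literally it does not provide for pneumococcal coverage at all. That is a wording error to correct in the same edit.

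**Conclusion.** The point holds as a defect in a secondary check. Appendix 1 permits reference coverage from dose counts or interviews while cases are classed from written records, contrary to its own same-source condition.

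At a true VE of 60% and coverage of 30% or 50%, the assumed dose-count errors move the screening VE up by 5 to 16 points or down by 14 to 20. The smallest of these shifts is at the top of the 2-5% range that Section 6.1 quotes from UK data. Against the 6.7 points that the Section 6.1 formula gives at VE 60%, or the 10% that it reports from the US simulation for a true VE of 70%, the shifts run from somewhat smaller to clearly larger. Either way, the check cannot reliably separate bias in the NVT controls from error in its own denominator.

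The sizes rest on assumed error rates and on correct case records. The direction at any site is unknown without data on its source.

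**What to change.** In Appendix 1, Vaccine coverage in the reference group:

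- Remove vaccine sales and distribution as a source for the validation estimate.
- Require person-level coverage in those aged 65 or over, from the same kind of record, with the same vaccine definition and for the same calendar period as the cases.
- Keep dose-count, interview or survey coverage only as a labelled sensitivity analysis that is not used to judge the NVT controls. Requiring cases to be classified by the same interview is not a workable alternative: some are severely ill or die, and it would replace the record-based ascertainment of Section 4.6.2.
- Change influenza to pneumococcal in the two list items that name it, and in the definition of the case proportion under Measure of effect.

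The cost is a few lines of text. Sites without record-based coverage lose this optional comparator as a validation.
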